### **9.3.3 Covariates**

Other covariates are described in [Table 1](#), including demographic information as available in the dataset as recorded at index date. Comorbidities included in the CCI will be identified during the pre-index period. Other and specific comorbidities such as cardiovascular conditions, cerebrovascular diseases, hypertension, diabetes, metabolic and endocrine comorbidities, anxiety and depression, gastro-esophageal reflux disease, cancer and obesity will also be identified during baseline. Additionally, polypharmacy at baseline, will be identified in the pre-index period. Finally, a composite measure of asthma control status will be made as defined in Table 1, classified as Well and Poor. Asthma Control Test score and eosinophil blood count levels as available, will also be identified at baseline for Cohort II only. We will also record exacerbation rate, resource use parameters, and cost during baseline.

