### 9.3.2 Outcomes

#### 9.3.2.1 Primary outcomes

*(Database I/II combined)*

The primary outcome measure is time to first exacerbation per person. Exacerbations will be defined as either a hospitalization with a primary diagnosis of asthma, an ER visit with a primary diagnosis of asthma, an asthma exacerbation diagnosis recorded (ICD 493.02, 493.12, 493.22, 493.92, J45.21, J45.31, J45.41, J45.51, J45.901). The primary endpoint analysis will be of patients aged 12 years and above.

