**Table 1: Matching Parameters**

Variable Name and Type	Description	Applicable to Study Cohort: 1=IMS, 2=EMRClaims+
ICS/LABA dose on ICS/LABAI date	The dose level of the first prescription on the ICS/LABAI date (low, medium, or high)	1 and 2
Demographics (categorical and continuous variables)	Age (10-year increments) and Gender Male/Female), Region (if available, Northeast, Midwest, South, West)	1 and 2
CCI (continuous variable)	Charlson Comorbidity Index score	1 and 2
Specific comorbidities (categorical variables)	Cardiovascular conditions, cerebrovascular diseases, hypertension, diabetes, metabolic and endocrine comorbidities, anxiety and depression, gastro-esophageal reflux disease, cancer and obesity identified using appropriate ICD codes. All above measures will be coded as binary (yes/no) variables.	1 and 2
Medications (categorical variable)	Polypharmacy level matched within a range of 2 drugs (for example, 0-2,3-5,6-8,8-10 and so on).	1 and 2
Asthma Control Status: Well Control or Poor Control (categorical variable)	‘Well Controlled’ if patient has no prescriptions for an OCS, and no asthma-related emergency department visits or hospitalizations other than the first diagnosis recorded in the data extracted (Ref: Stempel JACI 2005). Categories will include Well Controlled and Not Well Controlled.	1 and 2
Hospital admissions Outpatient visits ER visits and OCS use (categorical variables)	Poorly Controlled patients (“Not Well Controlled”) will further be matched based on the presence of asthma-related admissions, outpatient visits, and ER visits or use of OCS during the pre-index period.	1 and 2
Eosinophil levels (EMRClaims+ database only) (categorical variables)	Eosinophil level categories: <150 cells/μL, 151-300cells/μL, 301-400 cells/μL, ≥400 cells/μL (as available)	2
Asthma Control Test (ACT) results (EMRClaims+ database only) (categorical variables)	ACT score categories developed based on data distribution (as available)	2

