## **9.4 DATA SOURCES**

Two separate databases will be appended to create the analytic dataset to obtain sufficient power for the primary endpoint analysis. This approach will provide both comprehensive geographic representation from national claims, and important asthma clinical measures available through electronic medical records (EMR). Both databases have been widely published in the academic asthma literature.

As a general note, this study protocol attempts to anticipate availability of detailed data elements of the two real-world data sets listed below. Consistent with accepted research standards using retrospective administrative data, evaluation of missing data and study variables is often required to ultimately finalize the study protocol as it relates to inclusion of covariates as well as secondary outcome measures.

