## **9.5 STUDY SIZE**

The expected number of asthma patients aged 12 years and above, without concurrent COPD, and continuous enrollment for 12 months prior to the Tiotropium Respimat® date is estimated to be approximately 2,100 to be matched to double (4200 patients) the number of NonTio patients resulting in a total N =6,300. Power calculation was conducted for the primary endpoint, time-to-first exacerbation by the end of the follow-up time. The calculation was based on detecting a significant treatment effect using Cox proportional hazard model. Estimates were obtained from the MEZZO trial comparing tiotropium 2.5 µg vs. salmeterol ([P15-01655](#)). Assuming 6.4% of patients in the control group followed

up for 5.5 months will have an exacerbation (based on the salmeterol group in the MEZZO study) and assuming a constant hazard rate, equating to an exponential rate parameter of 0.012 per month for the control group and 0.0096 per month for the Tio group, the power is calculated to be 77%. Using the Primo study, assuming 26.9% of patients in the control group followed up for 11 months will have an exacerbation (based on the Tio R 5 group in the 48-week study Primo) and assuming a constant hazard rate, equates to an exponential rate parameter of 0.028 per month in the control group and 0.0224 per month in the Tio group, the power is 98%. The Mezzo-derived power calculation likely underestimates the power since our study design includes sicker patients that required a step-up in ICS treatment (not required in the Mezzo Study). While we expect that the actual power will lie between the two estimates (assuming that the patient population is similar to the less severe Primo patients and the more severe MEZZO patients), the estimated power is greater than 77%.

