## **9.7 DATA ANALYSIS**

### **9.7.1 Main analysis**

We will provide the sample attrition at each step of the inclusion-exclusion criteria as well as a baseline demographic and comorbidity breakdown. We will provide a comparative breakdown in baseline measures for the unmatched and matched cohorts to assess if PSM eliminated baseline differences. For the primary endpoints analysis, we will calculate the time to first exacerbation per patient and compare it between the two groups (Tio vs. NonTio). For secondary endpoint analyses we will compare the rate of exacerbation, proportion of patients with exacerbations after 6 months and one year (based on Kaplan Meier estimates), HCRU and average cost during follow-up and compare them between the two groups (Tio vs. NonTio).

The primary outcome of the study will be analyzed using Cox proportional hazard modelling. The secondary outcome of rate of exacerbation per patient will be analyzed using negative binomial regression. This technique works on the assumption that the rate of exacerbation varies among every subject in the study ([P16-06846](#)). Also this model accounts for overdispersion of data which is likely to happen due to variability between the patients. Balance in covariates will be checked after matching. If PSM was able to balance all observed baseline characteristics, the regression models for outcomes will be limited to the databases (IMS and EMR) and to the key independent variable of interest (namely Tio use vs. ICS/LABA dose increase) and model overfitting is not, therefore, of concern. However, if there are unbalanced baseline characteristics, we will include these characteristics in the regression as covariates. For regression model covariate selection we

will also estimate the multicollinearity of covariates by assessing their correlations of independent variables. For example, if comorbidities from the specific list are also included in CCI, they will only be included in the CCI.

In order to handle missing data, in the PSM we will create a category variable (‘missing data’) for each covariate to ensure that patients with that variable and without that variable are respectively matched. Patients with missing prescription data required for classification of the treatment groups will be excluded. Patients with missing lung function scores and ACT scores at baseline and in the follow up period will be excluded from these respective secondary analyses.

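### The recorded baseline exacerbation rate is not a matching variable and enters the outcome models only if judged unbalanced: a small residual gap that is cheap to close

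*Combined protocol and SAP*

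**What the plan says.** Section 9.3.3 (Covariates) states: "We will also record exacerbation rate, resource use parameters, and cost during baseline". It does not define that rate.

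Table 1 (Matching Parameters) has no row for an exacerbation count or rate. Two rows deal with prior events:

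- **Asthma control status** is binary. A patient is Well Controlled with "no prescriptions for an OCS, and no asthma-related emergency department visits or hospitalizations other than the first diagnosis recorded in the data extracted".
- **Event history** applies to Not Well Controlled patients only, who are further "matched based on the presence of asthma-related admissions, outpatient visits, and ER visits or use of OCS during the pre-index period".

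Other rows act as proxies: ICS/LABA dose at initiation, polypharmacy ("Polypharmacy level matched within a range of 2 drugs") and, in Database II where available, eosinophils and ACT score. Section 9.12 also names the number of prescriptions, overall and for asthma, among the matching measures.

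Section 9.3.2.1 counts as an exacerbation an asthma hospitalization, an asthma ER visit, or "an asthma exacerbation diagnosis recorded".

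Section 9.7.1 makes the outcome models depend on a balance check. "If PSM was able to balance all observed baseline characteristics", they contain only treatment and database; unbalanced characteristics are added as covariates. No threshold for imbalance is given.

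**The concern.** The pre-index exacerbation count is the baseline version of the outcome, so it is an obvious candidate confounder. A variable left out of the propensity score is balanced only as far as it correlates with the variables in it.

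Section 9.12 regards channeling as very probable and expects Tio patients, before matching, to be sicker and less well controlled. Section 9.9 adds that some Tio patients whose asthma is deteriorating will be matched to patients who simply continue high-dose ICS/LABA. For those matches, control of prior severity rests largely on the propensity score.

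At stake is a modest bias in the Cox hazard ratio and in the negative binomial rate ratio. If the imbalance remaining after matching follows the expected channeling, the bias works against Tio. The direction after matching is not certain.

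**Working it through.** **Step 1. Compare the outcome definition with the matching variables.**

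| Prior history | Section 9.3.2.1 | Table 1 |
|---|---|---|
| One asthma ER visit versus several | One event versus several | Same: Not Well Controlled, ER visit present |
| Exacerbation code with no OCS, ED visit or admission | Counts as an exacerbation | Well Controlled; no further matching on events |
| Number of exacerbations | Basis of the rate outcome | Not listed |

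Table 1 also exempts an ED visit or admission that is the first recorded diagnosis. This affects a pre-index count only if that diagnosis falls inside the look-back, so I give it no weight.

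**Step 2. Follow the recorded rate through Section 9.7.1.** On a plain reading it is an observed baseline characteristic, so it is checked after matching. If it is called unbalanced, it is added to the models. If it is called balanced, it is left out. Only the difference that passes the check can bias the result.

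**Step 3. The plan's own effect size (Section 9.5).** The rates reproduce:

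- −ln(1 − 0.064)/5.5 = 0.0120 per month
- −ln(1 − 0.269)/11 = 0.0285 per month (the plan uses 0.028)

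The first scenario is stated as "equating to an exponential rate parameter of 0.012 per month for the control group and 0.0096 per month for the Tio group", so HR = 0.0096/0.012 = 0.80. The second gives 0.0224/0.028 = 0.80.

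**Step 4. Illustrate the residual bias.** The documents give no baseline exacerbation distribution by group, so these inputs are assumptions:

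- Risk ratio per prior event (RR): 1.2 to 1.5.
- Standardized difference that passes the check (d): at most 0.10.
- SD of the count: either 1, or a Poisson value from the Section 9.5 control rates over 12 months. The latter is √(12 × 0.012) = √0.144 = 0.38 to √(12 × 0.028) = √0.336 = 0.58.

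Bias factor = RR^(d × SD). Apparent HR = 0.80 × factor.

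| SD | d | Factor | Apparent HR |
|---|---|---|---|
| 1 | 0.10 | 1.2^0.10 = 1.018 to 1.5^0.10 = 1.041 | 0.815 to 0.833 |
| 0.38 to 0.58 | 0.10 | 1.2^0.038 = 1.007 to 1.5^0.058 = 1.024 | 0.806 to 0.819 |
| 1 | 0.052 | 1.2^0.052 = 1.010 to 1.5^0.052 = 1.021 | 0.808 to 0.817 |

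The last row is the largest difference that a two-sided 5% test would leave unflagged with 2,100 versus 4,200 patients: 1.96 × √(1/2100 + 1/4200) = 1.96 × 0.0267 = 0.052.

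As a share of the planned log HR, ln(1/0.80) = 0.223, the first row is 0.0182/0.223 = 8% to 0.0405/0.223 = 18%.

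If the imbalance runs the other way, divide by the factor. The first row becomes 0.80/1.018 = 0.786 to 0.80/1.041 = 0.768.

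**The case against.** The strongest reply is that Section 9.7.1 already handles this: the rate is recorded, compared after matching and adjusted for if unbalanced. On that view only the choice between conditional and unconditional adjustment remains, and the real defect is the missing balance threshold, which affects every covariate. Much of this stands. It is why the point is confined to differences that pass the check. It does not remove the point, because with no stated trigger the main baseline predictor of the outcome can be left out of both the matching and the models.

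The proxies also deserve credit. Repeated OCS courses would raise a prescription count, so control is not purely by presence or absence. Well Controlled patients have, by definition, almost none of the events that further matching would use. The uncounted exacerbation code is an exception of unknown frequency.

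A reader might infer that prior exacerbations are uncontrolled, or that the hazard ratio could be badly distorted. The documents support neither. A standardized difference of 0.25, for example, would be 0.25/0.0267 = 9.4 standard errors from zero. It would pass only a lenient rule that the plan does not state.

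**Conclusion.** The gap is real but residual, and closing it is a cheap improvement. The recorded baseline exacerbation rate is absent from Table 1, its substitutes do not distinguish one prior event from several or follow the outcome definition fully, and a difference called balanced is left unadjusted.

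The documents do not allow the bias to be calculated, and it is probably small. On the assumptions shown, the planned HR of 0.80 would shift by no more than about 0.01 to 0.03, in either direction. This rests on the assumed risk ratio per event, the 0.10 limit and the SD. The Poisson SD uses control-group rates from the cited trials; overdispersion or higher pre-index rates would bring it closer to 1. The reading that the balance check covers the recorded rate is also an inference from the wording of Section 9.7.1.

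**What to change.** 1. Add the pre-index exacerbation count to the Table 1 propensity-score variables in both databases. Use the Section 9.3.2.1 definition over the look-back actually used (12 months, or 6 if the Section 9.11 fallback is invoked), in categories such as 0, 1, 2, and 3 or more. Report its standardized difference after matching.
2. Pre-specify the count as a covariate in the Cox and negative binomial models whatever the balance check shows, and report the treatment-plus-database model alongside.
3. If control status or the presence-of-event items also enter a model as unbalanced, apply the multicollinearity rule of Section 9.7.1 to the overlap, since they share events with the count.

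**Cost.** Low. No new data source is needed, and Section 9.4 leaves room for the change: "evaluation of missing data and study variables is often required to ultimately finalize the study protocol as it relates to inclusion of covariates". There is a small derivation step if the recorded rate uses another definition, and slightly fewer patients may find matches within the caliper. The hazard ratio becomes conditional on the count (hazard ratios are non-collapsible), which is why the simpler model is reported too.

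Overfitting is not a worry. Even at the lower Section 9.5 rates and an assumed 5.5 months of follow-up, expected events are 4200 × (1 − e^(−0.012 × 5.5)) + 2100 × (1 − e^(−0.0096 × 5.5)) = 268 + 108 = 376, against three extra parameters.

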**Table 1: Matching Parameters**

Variable Name and Type	Description	Applicable to Study Cohort: 1=IMS, 2=EMRClaims+
ICS/LABA dose on ICS/LABAI date	The dose level of the first prescription on the ICS/LABAI date (low, medium, or high)	1 and 2
Demographics (categorical and continuous variables)	Age (10-year increments) and Gender Male/Female), Region (if available, Northeast, Midwest, South, West)	1 and 2
CCI (continuous variable)	Charlson Comorbidity Index score	1 and 2
Specific comorbidities (categorical variables)	Cardiovascular conditions, cerebrovascular diseases, hypertension, diabetes, metabolic and endocrine comorbidities, anxiety and depression, gastro-esophageal reflux disease, cancer and obesity identified using appropriate ICD codes. All above measures will be coded as binary (yes/no) variables.	1 and 2
Medications (categorical variable)	Polypharmacy level matched within a range of 2 drugs (for example, 0-2,3-5,6-8,8-10 and so on).	1 and 2
Asthma Control Status: Well Control or Poor Control (categorical variable)	‘Well Controlled’ if patient has no prescriptions for an OCS, and no asthma-related emergency department visits or hospitalizations other than the first diagnosis recorded in the data extracted (Ref: Stempel JACI 2005). Categories will include Well Controlled and Not Well Controlled.	1 and 2
Hospital admissions Outpatient visits ER visits and OCS use (categorical variables)	Poorly Controlled patients (“Not Well Controlled”) will further be matched based on the presence of asthma-related admissions, outpatient visits, and ER visits or use of OCS during the pre-index period.	1 and 2
Eosinophil levels (EMRClaims+ database only) (categorical variables)	Eosinophil level categories: <150 cells/μL, 151-300cells/μL, 301-400 cells/μL, ≥400 cells/μL (as available)	2
Asthma Control Test (ACT) results (EMRClaims+ database only) (categorical variables)	ACT score categories developed based on data distribution (as available)	2

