### **9.1 STUDY DESIGN**

Data extraction from both databases (I and II, see [section 9.4](#)) will be conducted by

. All patients will be required to have a prescription for ICS/LABA therapy [e.g. Advair (Diskus and HFA), Airduo, Breo, Dulera, or Symbicort]. The date of the first prescription of ICS/LABA within the study period (Jan 1st 2016 to Nov 30th 2018) will be defined as ICS/LABA-initiation (ICS/LABAi) date. This baseline cohort will then be followed to identify two cohorts (two arms of the study). One cohort that receives a prescription for Tiotropium Respimat® 1.25 mcg (on top of baseline ICS/LABA) will be classified as the ‘Tio’ group, and the second cohort that receives a “step-up” from baseline low-dose ICS/LABA to medium/high dose ICS/LABA or from baseline medium dose ICS/LABA to high dose ICS/LABA or an additional prescription/refill of high-dose-ICS/LABA following the first prescription of baseline high dose ICS/LABA within the study period, will be classified as the ‘NonTio’ group. The date of the first prescription for Tiotropium Respimat® 1.25 mcg in the ‘Tio’ group will be defined as the index date for the ‘Tio’ group. Similarly the date of the first prescription for a “step-up” from baseline low-dose ICS/LABA to medium/high dose ICS/LABA or from baseline medium dose ICS/LABA to high dose ICS/LABA or an additional prescription/refill of high-dose-ICS/LABA following the first prescription of baseline high dose ICS/LABA (evidenced by at least 90-days of prescription utilization) within the study period will be defined as the index date for the ‘NonTio’ group.

Patients will be required to have a minimum follow-up period of 30 days after the index date for the analyses of the primary endpoint with no limit on the maximum period (this 30-day minimum follow-up period requirement will be waived in a sensitivity analysis). Subject to sample size requirements, patients will be required to have available records for at least 12 months prior to the index date to ensure no prior use of Tiotropium Respimat® and to establish baseline patient characteristics. This 12-month period prior to the index date will be defined as the pre-index period.

Figure 9.1.1 Study Design

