### **IMS Pharmetrics (IMS or Database I)**

We will establish Database 1 using medical and pharmacy claim records from IMS Pharmetrics data. Data from January 2015-2018 will be extracted, with the first patient follow-up period for tiotropium 1.25 mcg dose patients starting January 2016. This database contains administrative insurance data and enrolment information derived from approximately 150 million commercially insured and Medicare lives. This longitudinal database allows documentation and analysis of the patient journey from diagnosis to intervention and follow-up. It is nationally representative covering 90% of US hospitals and compliant with current HIPAA (Health Insurance Portability and Accountability Act) regulations.

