## 9.11 SUBJECTS

1. Patients with least one asthma diagnosis in the inpatient setting or at least two separate instances of asthma diagnosis (separated by at least 30 days) recorded in the outpatient or emergency room setting will be included (ICD 9 CM: 493.xx or ICD 10: J45-J45.999).
2. Patients will be required to be already on ICS/LABA.
3. Patients below the age of 6 years on the ICS/LABAI date will be excluded.
4. Patients will be required to have available records 12 months prior to the index date (6 months will be used if patient exclusions due to this criteria adversely affect the study sample size).
5. Patients with a diagnosis of COPD at any time during the study period will be excluded.
6. Those who are on biologics at baseline will be removed.
7. After the PSM process, unmatched patients will be excluded.

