## 9.12 BIAS

### Channeling Bias Mitigation

Introduction of channeling bias in this study is highly likely using retrospective claims data based on asthma medication use; patients between the two cohorts may differ in baseline control and severity levels. On aggregate, patients for whom Tiotropium Respimat® 1.25 mcg was added (vs NonTio) are likely to be less well-controlled and more severe both at baseline and during the follow up period. Absent a method to control for this channeling bias, it is likely that placing sicker patients in the Tiotropium Respimat® 1.25mcg group will confound an accurate comparison of cost, resource use, and other outcomes between the groups. Two design features of our study will help mitigate this bias. First, our comparison (NonTio) group will be required to step-up their baseline ICS/LABA dose or have an additional prescription/refill of high-dose-ICS/LABA following the first prescription of baseline high dose ICS/LABA within the study period. Second, we will use Propensity Score Matching (PSM) to match patients on key measures of disease control and severity as listed in [Table 1](#), such as demographics, Charlson Comorbidity Index (CCI) score, specific comorbidities, number of prescriptions (overall and asthma-related medications). This baseline matching strategy will be particularly important to ensure that patients in the TIO group who have a corresponding increase in their ICS dose at or prior to the date of their TIO prescription (for example, if the patient has an exacerbation), will be matched to a corresponding NonTIO patient in terms of increased ICS dose or additional ICS prescription. It should be noted that after the prescription index date for both Tio and NonTio patients, we anticipate changes in ICS medication for patients in both cohorts. These ICS medication changes reflect patient

outcomes in the follow-up period, where patients who encounter exacerbation in either group are likely to see a change in the ICS dose.

As a result, post-index period ICS medication changes will not alter the classification of patient groups nor will it be the basis for exclusion of these patients.

We will conduct 1:2 matching using a nearest neighbour matching approach with a radius of  $0.2 * SD(\log(P))$ . This will be conducted in both databases (IMS: Cohort I and EMRClaims+: Cohort II) separately.

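### The matching variables omit calendar time of index, although the high-dose refill rule ties part of the NonTio index dates to soon after the first ICS/LABA fill in the window

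*Combined protocol and SAP*

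**What the plan says.** **Matching variables.** "Table 1: Matching Parameters" (section 9.3.3) lists ICS/LABA dose at the first fill, age, gender, region, CCI, specific comorbidities, polypharmacy, control status, asthma-related use and OCS and, in Database II, eosinophils and ACT. Section 9.12 restates the list: "such as demographics, Charlson Comorbidity Index (CCI) score, specific comorbidities, number of prescriptions (overall and asthma-related medications". Neither names index date, year, quarter or season.

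**Matching method.** Section 9.12: "We will conduct 1:2 matching using a nearest neighbour matching approach with a radius of" 0.2 times the SD of log(P), run separately in each database.

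**Anchor.** The ICS/LABAi date in section 9.1 is "The date of the first prescription of ICS/LABA within the study period" (1 January 2016 to 30 November 2018), and no washout is stated. Section 9.11 adds: "Patients will be required to be already on ICS/LABA".

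**Index date (section 9.1).** Tio patients are indexed at their first Tio prescription. NonTio patients are indexed at their first dose step-up or, if on high dose at baseline, at "an additional prescription/refill of high-dose-ICS/LABA following the first prescription of baseline high dose ICS/LABA (evidenced by at least 90-days of prescription utilization").

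**Follow-up and models.** Follow-up is at least 30 days with no upper limit (section 9.1). Section 9.7.1 uses Cox regression for the primary outcome, Kaplan-Meier for the 6-month and one-year proportions, negative binomial regression for the exacerbation rate with no offset stated, and a comparison of HCRU and average cost over follow-up with no time unit stated. Covariates enter the models only if they are baseline characteristics left unbalanced by matching.

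**The concern.** The two groups do not reach their index dates in the same way. A baseline high-dose patient has no higher dose level to step up to, so the only way into NonTio is the refill rule, "an additional prescription/refill of high-dose-ICS/LABA following the first prescription of baseline high dose ICS/LABA". That date follows the ICS/LABAi date closely. For patients already on treatment when the window opens, the ICS/LABAi date itself will tend to fall early in 2016. A Tio prescription can come at any time up to November 2018.

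If the groups are indexed in different parts of a 35-month window, they are compared in different seasons and years, and the earlier group can be observed for longer. Nothing in the matching or the default models would detect or correct this. At stake are some confounding of the primary hazard ratio and, if HCRU and cost are compared as totals, a difference produced by observation time alone.

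**Working it through.** The plan gives no figure for index dates or follow-up by group, so there is none to reproduce on this point. The sizes below are illustrations on assumed inputs.

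**1. Which index dates are tied to an early date?**
- Tio: first prescription at any time after ICS/LABAi. Not tied.
- NonTio, step-up route: first step-up at any time after ICS/LABAi. Not tied.
- NonTio, refill route: the next high-dose refill. Tied to shortly after ICS/LABAi.

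The shift therefore comes from one of the two NonTio routes, and its share *s* is not stated.

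**2. Follow-up ratio as a function of *s*.** From section 9.1: a 35-month window and a 30-day minimum. Assumed: Tio and step-up dates uniform over the first 34 months, refill dates uniform over months 0 to 4, and disenrolment at 2% per month. For potential follow-up F, mean observed follow-up is (1 − E[e^(−0.02F)]) / 0.02.
- Tio and step-up, F uniform on 1 to 35: E = (e^−0.02 − e^−0.70) / (0.02 × 34) = 0.711, so the mean is 0.289 / 0.02 = 14.4 months.
- Refill, F uniform on 31 to 35: E = (e^−0.62 − e^−0.70) / (0.02 × 4) = 0.517, so the mean is 0.483 / 0.02 = 24.2 months.
- Ratio NonTio to Tio = [s × 24.2 + (1 − s) × 14.4] / 14.4.

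| Refill share | Mean NonTio follow-up (months) | Ratio to Tio |
|---|---|---|
| 0% | 14.4 | 1.00 |
| 25% | 16.9 | 1.17 |
| 50% | 19.3 | 1.34 |
| 100% | 24.2 | 1.67 |

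A second set-up placed refills 1 to 3 months after ICS/LABAi, with 0%, 50% or 80% of ICS/LABAi dates in the first three months. It gave 1.00, 1.15 to 1.17, 1.31 to 1.34 and 1.61 to 1.66 at the same shares.

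**3. Primary hazard ratio when the true value is 1.00.** The control hazard of 0.028 per month is from section 9.5, and it follows from the figures there: −ln(1 − 0.269) / 11 = 0.0285. The planned effect is 0.0224 / 0.028 = 0.80.
- *Season.* Assumed: a sinusoidal swing of 20% to 40% around the mean hazard, with an autumn or winter peak. Across the set-ups simulated, the Cox hazard ratio ran from about 0.97 to 1.06. At a 50% refill share it ran from about 0.99 to 1.04.
- *Trend.* The documents describe none. If the hazard changed by 5% to 10% per year and mean index dates differed by 6 months, the ratio would be (1 + trend)^0.5: 0.95^0.5 = 0.975 and 0.90^0.5 = 0.949 if falling, 1.05^0.5 = 1.025 and 1.10^0.5 = 1.049 if rising.
- *Against the planned effect on the log scale:* ln 0.97 / ln 0.80 = 14% in Tio's favour; ln 1.06 / |ln 0.80| = 26% against Tio.

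**4. HCRU and cost.** If both groups used resources at the same monthly rate and were compared on totals, Tio would appear lower by 1 − 1/ratio: 14% at a 25% share, 25% at 50% and 40% at 100%.

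**The case against.** The strongest case against is that the plan reports no index-date distribution. Step-up dates behave like Tio dates, so if few NonTio patients enter by the refill route and Tio uptake is flat, there is no gap. This stands: an imbalance is likely but not demonstrated, and ratios of 1.3 to 1.7 need a refill share of roughly 50% to 100%.

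A reader might infer that season, calendar trend and follow-up do differ by group, that this favours Tio, or that it could explain a large part of the planned effect. The documents support none of these. The illustrative hazard ratios fall on both sides of 1, the larger departure in the seasonal simulations is against Tio, and no trend in the hazard is documented. Nor does section 9.4 show that Tio dates come later. Its statement "with the first patient follow-up period for tiotropium 1.25 mcg dose patients starting January 2016" gives only the earliest possible date.

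Unequal follow-up does not by itself bias Cox or Kaplan-Meier estimates when censoring is non-informative. The HCRU and cost problem is a missing time unit, which matching on calendar time would not supply. Both points stand and narrow the concern.

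Finally, section 9.4 allows covariates to be finalised after data review, and section 9.7.1 adds unbalanced baseline characteristics to the models. Neither names calendar time, so the gap is softened but not closed.

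**Conclusion.** The concern holds in a limited form. Calendar time of index is missing from the matching list, from section 9.12 and from the default outcome models, while one NonTio route is tied by rule to an early date and Tio is not. A difference in index date and potential follow-up is therefore likely, and its size depends on the unstated refill share: a follow-up ratio of about 1.0 at 0%, 1.17 at 25%, 1.3 at 50% and 1.6 to 1.7 at 100%. These figures rest on assumed uniform Tio and step-up dates, refills soon after ICS/LABAi and 2% monthly disenrolment.

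For the primary hazard ratio the effect is modest, within about 0.97 to 1.06 under the assumed seasonal swings, and its direction cannot be derived. HCRU and cost are more exposed, but only if they are compared without regard to observation time, which the plan leaves open.

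**What to change.** 1. Add index calendar year and quarter to the Table 1 list as propensity-score covariates, in both databases.
2. Report their balance before and after matching, and the follow-up distribution by group. State the share of NonTio patients who enter by the refill route.
3. Count index year and quarter among the baseline characteristics that enter the outcome models if still unbalanced.
4. Separately, analyse HCRU and cost per unit of person-time, and include log person-time as an offset in the negative binomial model. Calendar matching alone does not equalise observed follow-up.

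Do not make quarter and year an exact-match stratum. If NonTio dates did cluster in the first 3 to 6 of 35 months and Tio dates were spread evenly, 1 − 6/35 = 83% to 1 − 3/35 = 91% of Tio patients would fall outside that period and have no control from the same quarter.

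The cost is small. The index date is already derived for every patient, so no new data are needed. Some Tio patients may lose a match, which would reduce the planned 2,100 to 4,200 allocation; report how many do.
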